5. INVESTIGATIONAL PRODUCTS

For the purposes of this study, and per International Council for Harmonisation (ICH) guidelines, investigational product is defined as a pharmaceutical form of an active ingredient or placebo being tested or used as a reference/comparator in a clinical trial, including a product with a marketing authorization when used or assembled (formulated or packaged) in a way different from the approved form, or when used for an unapproved indication, or when used to gain further information about an approved use (ICH E6 1.33).

For this study, the investigational products are 13vPnC with 2-PE in MDVs and 13vPnC without 2-PE in PFSs.

5.1. Allocation to Investigational Product

The investigator's knowledge of the investigational product should not influence the decision to randomize a particular subject or affect the order in which subjects are randomized.

Allocation of subjects to vaccine groups will proceed through the use of an interactive response technology (IRT) system (interactive web-based response [IWR]). The site personnel (study coordinator or specified designee) will be required to enter or select information including but not limited to the user's identification (ID) and password, the protocol number, and the subject number. The site personnel will then be provided with a vaccine assignment, randomization number, and dispensable unit (DU) or container number when investigational product is being supplied via the IRT system. The IRT system will provide a confirmation report containing the subject number, randomization number, and DU or container number assigned. The confirmation report must be stored in the site's files.

The study-specific IRT reference manual will provide the contact information and further details on the use of the IRT system.

5.2. Subject Compliance

All doses of investigational product will be administered by the appropriately designated study staff at the investigator site.

5.3. Investigational Product Supplies

5.3.1. Dosage Form(s) and Packaging

13vPnC will be provided to the study site by the sponsor in MDVs and single-dose PFSs.

13vPnC contains saccharides from pneumococcal serotypes 1, 3, 4, 5, 6A, 6B, 7F, 9V, 14, 18C, 19A, 19F, and 23F individually conjugated to nontoxic diphtheria toxin CRM₁₉₇. The

vaccine is formulated to contain 2.2 µg of each saccharide, except for 4.4 µg of 6B, per 0.5-mL dose. The vaccine is formulated with 5 mM succinate buffer, 0.02% polysorbate 80, and 0.125 mg of aluminum as aluminum phosphate, per 0.5-mL dose.

13vPnC MDVs will also contain 4 mg of 2-PE per 0.5-mL dose. Four (4) doses of 13vPnC (2.0 mL) will be contained within each MDV. For the purposes of this study, only a single 0.5-mL dose will be administered from each of the MDVs.

5.3.2. Concomitant Study Vaccines

The following mandatory vaccines will be administered concomitantly with the investigational product as detailed in the schedule of activities:

- DTP-Hib-HBV
- Rotavirus vaccine
- Hepatitis A virus vaccine

DTP-Hib-HBV will be administered intramuscularly at 6, 10, and 14 weeks of age.

Rotavirus vaccine will be administered orally at 6, 10, and 14 weeks of age.

Hepatitis A virus vaccine will be administered intramuscularly at 12 months of age.

The SRSD for DTP-Hib-HBV, rotavirus vaccine, or hepatitis A virus vaccine is the local package insert.

5.4. Concomitant Medication(s)/Treatment(s)

5.4.1. Prior Treatment

Vaccines given at birth or before enrollment, including bacillus Calmette-Guerin (BCG) vaccine, hepatitis B virus (HBV) vaccine, or polio vaccine, may be given as per local recommendations.

All vaccinations received from birth until enrollment into the study will be recorded on the case report form (CRF).

5.4.2. Prohibited Vaccines and Medications

No pneumococcal vaccines (licensed or investigational) other than those described in this study may be given prior to or during the study.

Local anesthetic cream should not be used at the site of investigational product administration.

Prophylactic use of antipyretic and other pain medications to prevent symptoms that might occur as a result of study vaccine administration should be discouraged; however, it is

recognized that use of antipyretic medication is a matter of parental choice and local clinical practice.

5.4.3. Permitted Vaccines and Medications

In addition to the mandatory vaccines given concomitantly with the investigational product, other vaccines, including polio vaccine, may be administered as per local recommendations at any time. Vaccines concomitantly administered with the investigational product must be given in a different limb from that used to administer 13vPnC. All vaccinations received during the study will be recorded on the CRF.

Topical and inhaled corticosteroids are permitted during the course of the study.

Local anesthetic cream may be applied before the blood draws.

Antipyretic and other pain medications to treat symptoms are permitted.

Any medications, except those listed in [Section 5.3.2](#), are permitted.

Details of any medication(s) given will not be collected in the CRF.

5.5. Preparation and Dispensing

Only qualified personnel should dispense the investigational products.

See the Investigational Product Manual (IP manual) or equivalent for instructions on how to prepare the investigational product for administration. Investigational product should be prepared and dispensed by an appropriately qualified and experienced member of the study staff (eg, physician, nurse, physician's assistant, nurse practitioner, pharmacy assistant/technician, or pharmacist) as allowed by local, state, and institutional guidance.

5.6. Administration

Subjects will receive 1 dose of 13vPnC at each vaccination visit (Visits 1, 2, 3, and 5) in accordance with the study's schedule of activities.

13vPnC should be administered intramuscularly by injecting 0.5 mL into the anterolateral thigh muscle of the left leg at the vaccination visits.

For the purposes of this study, only a single 0.5-mL dose will be administered from each of the MDVs.

For DTP-Hib-HBV, rotavirus vaccine, and hepatitis A virus vaccine, dosage recommendations in the appropriate locally approved labeling should be followed. Concomitant vaccines must be given in a different limb from that used to administer 13vPnC.

Standard vaccination practices must be observed and vaccine must not be injected into blood vessels. Appropriate medication and other supportive measures for management of an acute

hypersensitivity reaction should be available in accordance with local guidelines for standard immunization practices.

Administration of investigational products should be performed by an appropriately qualified, Good Clinical Practice (GCP)-trained, and vaccine-experienced member of the study staff (eg, physician, nurse, physician's assistant, nurse practitioner, pharmacist, or medical assistant) as allowed by local, state, and institutional guidance.

Investigational product administration details will be recorded on the CRF.

5.7. Investigational Product Storage

The investigator or an approved representative, eg, pharmacist, will ensure that all investigational products and other mandatory study vaccines, including DTP-Hib-HBV, rotavirus vaccine, and hepatitis A virus vaccine, are stored in a secured area with controlled access under required storage conditions and in accordance with applicable regulatory requirements.

Investigational products should be stored in their original containers and in accordance with the labels.

Any storage conditions stated in the SRSD will be superseded by the storage conditions stated on the product label.

Site systems must be capable of measuring and documenting (for example, via a log), at a minimum, daily minimum and maximum temperatures for all site storage locations (as applicable, including frozen, refrigerated, and/or room-temperature products). This should be captured from the time of investigational product receipt throughout the study. Even for continuous-monitoring systems, a log or site procedure that ensures active evaluation for excursions should be available. The intent is to ensure that the minimum and maximum temperature is checked each business day to confirm that no excursion occurred since the last evaluation and to provide the site with the capability to store or view the minimum/maximum temperature for all nonworking days upon return to normal operations. The operation of the temperature-monitoring device and storage unit (for example, refrigerator), as applicable, should be regularly inspected to ensure they are maintained in working order.

Any excursions from the product label storage conditions should be reported to Pfizer upon discovery. The site should actively pursue options for returning the product to the storage conditions described in the labeling, as soon as possible. Deviations from the storage requirements, including any actions taken, must be documented and reported to Pfizer.

Once an excursion is identified, the investigational product must be quarantined and not used until Pfizer provides permission to use the investigational product. It will not be considered a protocol deviation if Pfizer approves the use of the investigational product after the temperature excursion. Use of the investigational product prior to Pfizer approval will be considered a protocol deviation. Specific details regarding information the site should report for each excursion will be provided to the site.

Receipt of materials, door opening and closing, and other routine handling operations where the products are briefly out of the temperature range described in the labeling are not considered excursions.

5.8. Investigational Product Accountability

The investigator site must maintain adequate records documenting the receipt, use, loss, or other disposition of the investigational product supplies. All investigational products will be accounted for using a drug accountability form/record.

5.8.1. Destruction of Investigational Product Supplies

The sponsor or designee will provide guidance on the destruction of unused investigational product (eg, at the site). If destruction is authorized to take place at the investigator site, the investigator must ensure that the materials are destroyed in compliance with applicable environmental regulations, institutional policy, and any special instructions provided by Pfizer, and all destruction must be adequately documented.

6. STUDY PROCEDURES

6.1. Study Period

Visit windows are included in this protocol so that subjects in this study all have their vaccinations and blood draws within a broadly uniform time frame. However, because of the population under study, it is recognized that it may not always be possible to adhere to these windows (for example, because of subject illness).

6.1.1. Infant Series (6, 10, and 14 Weeks of Age)

6.1.1.1. Visit 1 (42 to 72 Days of Age)

- Obtain informed consent per local requirements from the subject's parent(s)/legal guardian(s) before performing study-specific procedures.
- Record the subject's demographic information (including date of birth, sex, and ethnicity).
- Obtain and record the subject's medical history including prior vaccinations.
- Perform a physical examination evaluating any clinically significant abnormalities within the following body systems: general appearance; skin; head, eyes, ears, nose, and throat; heart; lungs; abdomen; extremities; neurological; musculoskeletal; and lymph nodes; including worsening of medical history conditions.
- Weigh the subject.
- Ensure that all inclusion criteria, none of the exclusion criteria, and none of the temporary delay criteria are met.

- On the day of vaccination, prior to vaccination, measure and record the subject's axillary temperature.
- After all entry criteria are confirmed, the subject will be randomized into 1 of the 2 vaccine groups using an IRT system (IWR), or equivalent system. An appropriate site staff member will use the IRT system to obtain the subject's investigational product DU or container number.
- Administer a single 0.5-mL intramuscular injection of 13vPnC from either an MDV or a PFS into the anterolateral thigh muscle of the left leg.
- Administer a single intramuscular dose of DTP-Hib-HBV into a different limb from that used to administer 13vPnC, according to local clinical practice.
- Administer a single dose of rotavirus vaccine according to local clinical practice.
- Observe the subject for at least 30 minutes after vaccination for any significant acute reactions. Any AEs noted during the observation period should be recorded in the subject's source documents and on the AE section of the CRF.
- Issue a caliper and a digital thermometer to the parent(s)/legal guardian(s)/caregiver(s) and provide instructions on their use.
- Issue a subject electronic diary (e-diary) to the parent(s)/legal guardian(s)/caregiver(s). Provide instruction on its completion for 7 days (Day 1 through Day 7, where Day 1 is the day of vaccination).
- Ask the parent(s)/legal guardian(s)/caregiver(s) to contact the investigator immediately if any significant illness or hospitalization occurs during the study period, or if the subject experiences a large (>14 caliper units) local reaction.
- Schedule an appointment with the parent(s)/legal guardian(s)/caregiver(s) for the next study visit.
- Remind the parent(s)/legal guardian(s)/caregiver(s) to bring the e-diary to the next study visit.
- The investigator or an authorized designee completes the source documents, completes the CRF, and updates the investigational product accountability records.

6.1.1.2. Visit 2 (28 to 42 Days After Visit 1)

- Review the subject's e-diary data and follow up on any ongoing local reactions or systemic events.
- Based on clinical evaluation, determine whether any AEs or SAEs have occurred since the last study visit and record them on the CRF.

- Review AEs that were ongoing from the previous visit and record their end dates or confirm that they are still ongoing.
- Ensure that the subject continues to be eligible for the study and meets none of the withdrawal criteria ([Section 6.2](#)).
- On the day of vaccination, prior to vaccination, measure and record the subject's axillary temperature.
- Ensure that the subject does not meet any of the temporary delay criteria ([Section 4.3](#)).
- An appropriate site staff member will use the IRT system to obtain the subject's investigational product DU or container number.
- Administer a single 0.5-mL intramuscular injection of 13vPnC from an MDV or a PFS into the anterolateral thigh muscle of the left leg.
- Administer a single intramuscular dose of DTP-Hib-HBV into a different limb from that used to administer 13vPnC, according to local clinical practice.
- Administer a single dose of rotavirus vaccine according to local clinical practice.
- Observe the subject for at least 30 minutes after vaccination for any significant acute reactions. Any AE noted during the observation period should be recorded on the source documents and on the AE section of the CRF.
- Issue a caliper and a digital thermometer (if necessary) to the parent(s)/legal guardian(s)/caregiver(s) and provide instructions on their use.
- Issue a subject e-diary (if necessary) to the parent(s)/legal guardian(s)/caregiver(s). Provide instruction on its completion for 7 days (Day 1 through Day 7, where Day 1 is the day of vaccination).
- Ask the parent(s)/legal guardian(s)/caregiver(s) to contact the investigator immediately if any significant illness or hospitalization occurs during the study period, or if the subject experiences a large (>14 caliper units) local reaction.
- Schedule an appointment with the parent(s)/legal guardian(s)/caregiver(s) for the next study visit.
- Remind the parent(s)/legal guardian(s)/caregiver(s) to bring the e-diary to the next study visit.
- The investigator or an authorized designee completes the source documents, completes the CRF, and updates the investigational product accountability records.

6.1.1.3. Visit 3 (28 to 42 Days After Visit 2)

- Review the subject's e-diary and follow up on any ongoing local reactions or systemic events.
- Based on clinical evaluation, determine whether any AEs or SAEs have occurred since the last study visit and record them on the CRF.
- Review AEs that were ongoing from the previous visit and record their end dates or confirm that they are still ongoing.
- Ensure that the subject continues to be eligible for the study and meets none of the withdrawal criteria ([Section 6.2](#)).
- On the day of vaccination, prior to vaccination, measure and record the subject's axillary temperature.
- Ensure that the subject does not meet any of the temporary delay criteria ([Section 4.3](#)).
- An appropriate site staff member will use the IRT system to obtain the subject's investigational product DU or container number.
- Administer a single 0.5-mL intramuscular injection of 13vPnC from an MDV or a PFS into the anterolateral thigh muscle of the left leg.
- Administer a single intramuscular dose of DTP-Hib-HBV into a different limb from that used to administer 13vPnC, according to local clinical practice.
- Administer a single dose of rotavirus vaccine according to local clinical practice.
- Observe the subject for at least 30 minutes after vaccination for any significant acute reactions. Any AE noted during the observation period should be recorded on the source documents and on the AE section of the CRF.
- Issue a caliper and a digital thermometer (if necessary) to the parent(s)/legal guardian(s)/caregiver(s) and provide instructions on their use.
- Issue a subject e-diary (if necessary) to the parent(s)/legal guardian(s)/caregiver(s). Provide instruction on its completion for 7 days (Day 1 through Day 7, where Day 1 is the day of vaccination).
- Ask the parent(s)/legal guardian(s)/caregiver(s) to contact the investigator immediately if any significant illness or hospitalization occurs during the study period, or if the subject experiences a large (>14 caliper units) local reaction.
- Schedule an appointment with the parent(s)/legal guardian(s)/caregiver(s) for the next study visit.

- Remind the parent(s)/legal guardian(s)/caregiver(s) to bring the e-diary to the next study visit.
- The investigator or an authorized designee completes the source documents, completes the CRF, and updates the investigational product accountability records.

6.1.2. Post–Infant Series Visit (18 Weeks of Age)

6.1.2.1. Visit 4 (28 to 42 Days After Visit 3)

- Collect the subject's e-diary.
- Review the subject's e-diary data and follow up on any ongoing local reactions or systemic events.
- Based on clinical evaluation, determine whether any AEs or SAEs have occurred since the last study visit and record them on the CRF.
- Review AEs that were ongoing from the previous visit and record their end dates or confirm that they are still ongoing.
- Ensure that the subject continues to be eligible for the study and meets none of the withdrawal criteria ([Section 6.2](#)).
- Collect an approximately 5-mL blood sample.
- Schedule an appointment with the parent(s)/legal guardian(s)/caregiver(s) for the next study visit.
- The investigator or an authorized designee completes the source documents, and completes the CRF.

6.1.3. Toddler Dose (12 Months of Age)

6.1.3.1. Visit 5 (365 to 420 Days of Age)

- Based on clinical evaluation, determine whether SAEs or newly diagnosed chronic medical conditions have occurred since the last study visit and record them on the CRF.
- Review AEs that were ongoing from the previous visit and record their end dates or confirm that they are still ongoing.
- On the day of vaccination, prior to vaccination, measure and record the subject's axillary temperature.
- Ensure that the subject continues to be eligible for the study and meets none of the withdrawal criteria ([Section 6.2](#)).
- Ensure that the subject does not meet any of the temporary delay criteria ([Section 4.3](#)).

- An appropriate site staff member will use the IRT system to obtain the subject's investigational product DU or container number.
- Administer a single 0.5-mL intramuscular injection of 13vPnC from an MDV or a PFS into the anterolateral thigh muscle of the left leg.
- Administer a single dose of hepatitis A virus vaccine into a different limb from that used to administer 13vPnC, according to local clinical practice.
- Observe the subject for at least 30 minutes after vaccination for any significant acute reactions. Any AE noted during the observation period should be recorded on the source documents and on the AE section of the CRF.
- Issue a caliper and a digital thermometer to the parent(s)/legal guardian(s)/caregiver(s) and provide instructions on their use.
- Issue a subject e-diary to the parent(s)/legal guardian(s)/caregiver(s). Provide instruction on its completion for 7 days (Day 1 through Day 7, where Day 1 is the day of vaccination).
- Ask the parent(s)/legal guardian(s)/caregiver(s) to contact the investigator immediately if any significant illness or hospitalization occurs during the study period, or if the subject experiences a large (>14 caliper units) local reaction.
- Schedule an appointment with the parent(s)/legal guardian(s)/caregiver(s) for the next study visit.
- Remind the parent(s)/legal guardian(s)/caregiver(s) to bring the e-diary to the next study visit.
- The investigator or an authorized designee completes the source documents, completes the CRF, and updates the investigational product accountability records.

6.1.4. Post-Toddler Dose Visit (13 Months of Age)

6.1.4.1. Visit 6 (28 to 42 Days After Visit 5)

- Collect the subject's e-diary.
- Review the subject's e-diary data and follow up on any ongoing local reactions or systemic events.
- Based on clinical evaluation, determine whether any AEs or SAEs have occurred since the last study visit and record them on the CRF.
- Review AEs that were ongoing from the previous visit and record their end dates or confirm that they are still ongoing.

- Collect a blood sample (approximately 5 mL).
- The investigator or an authorized designee completes the source documents, and completes the CRF.

6.1.5. Unscheduled Visits

If a local reaction at the pneumococcal injection site is greater than 14 caliper units (7.0 cm), a study site visit will be required to assess the extent of the reaction. The subject's parent(s)/legal guardian(s)/caregiver(s) should contact the study personnel to arrange for an additional visit to the study site for assessment by the investigator or a medically qualified member of the investigator's staff, who will:

- Measure axillary temperature.
- Measure the minimum and maximum diameter of the redness or swelling in centimeters.
- Assess pain at the injection site (tenderness) in accordance with the criteria provided in [Section 7.1.2](#).
- Complete the CRF.
- If applicable, remind the subject's parent(s)/legal guardian(s)/caregiver(s) to enter an end date of the reaction in the e-diary.

For the purpose of assessments performed during unscheduled visits, a medically qualified member of study staff is a study physician or a study nurse, as applicable to the investigator's local practice.

6.2. Subject Withdrawal

An investigator and/or sponsor can withdraw a subject from the study if deemed appropriate. In addition, if a subject fails to continue to meet the inclusion criteria, new information becomes available that would exclude the subject, or the subject develops a condition or situation that would meet exclusion criteria, the subject may be considered for withdrawal.

Reasons why a subject may discontinue or be withdrawn from the study include, but are not limited to, failure to meet entrance criteria (screening failure), AE, death, protocol violation, lost to follow-up, no longer willing to participate in the study, study terminated by sponsor, investigator declined further study participation, or any other reason. Subjects who have received the investigational product will not be replaced regardless of the reason for withdrawal.

Lost to follow-up:

All reasonable efforts must be made to locate subjects to determine and report their ongoing status. Lost to follow-up is defined by the inability to reach the subject's parent(s)/legal guardian(s)/caregiver(s) after a minimum of 2 documented phone calls, faxes, or emails as

well as lack of response by the subject's parent(s)/legal guardian(s)/caregiver(s) to 1 registered mail letter. All attempts should be documented in the subject's medical records.

If it is determined that the subject has died, the site will use locally permissible methods to obtain the date and cause of death. The site staff and representative will consult publicly available sources, such as public health registries and databases, in order to obtain updated contact information. If, after all attempts, the subject remains lost to follow-up, then the last-known-alive date as determined by the investigator should be reported and documented in the subject's medical records.

The subject's parent(s)/legal guardian(s) may withdraw the subject from the study at any time at their own request, or the subject may be withdrawn at any time at the discretion of the investigator or sponsor for safety (see also the Withdrawal From the Study Due to Adverse Events section) or behavioral reasons, or the inability of the subject to comply with the protocol-required schedule of study visits or procedures at a given study site.

If a subject does not return for a scheduled visit, every effort should be made to contact the subject's parent(s)/legal guardian(s)/caregiver(s). All attempts to contact the subject's parent(s)/legal guardian(s)/caregiver(s) and information received during contact attempts must be documented in the subject's medical record. In any circumstance, every effort should be made to document subject outcome, if possible. The investigator should inquire about the reason for withdrawal, request that the subject return for a final visit, if applicable, and follow up with the subject's parent(s)/legal guardian(s)/caregiver(s) regarding any unresolved AEs.

If the subject's parent(s)/legal guardian(s) withdraw(s) the child from the study, and also withdraw(s) consent for disclosure of future information, no further evaluations should be performed, and no additional data should be collected. The sponsor may retain and continue to use any data collected before such withdrawal of consent.

Withdrawal of consent:

Subjects whose parent(s)/legal guardian(s) request(s) to discontinue receipt of investigational product will remain in the study and must continue to be followed for protocol-specified follow-up procedures. The only exception to this is when a subject's parent(s)/legal guardian(s) specifically withdraw(s) consent for any further contact with him or her or persons previously authorized by the subject's parent(s)/legal guardian(s) to provide this information. Subject's parent(s)/legal guardian(s) should notify the investigator in writing of the decision to withdraw consent from future follow-up, whenever possible. The withdrawal of consent should be explained in detail in the medical records by the investigator, as to whether the withdrawal is only from further receipt of investigational product or also from study procedures and/or posttreatment study follow-up. In the event that vital status (whether the subject is alive or dead) is being measured, publicly available information should be used to determine vital status only as appropriately directed in accordance with local law.

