2. STUDY OBJECTIVES AND ENDPOINTS

Primary Objective	Primary Endpoints
To describe the safety profile of 13vPnC with 2-PE in the MDV group and without 2-PE in the PFS group.	
 Incidence of local reactions and systemic events at the following time periods in the MDV group and in the PFS group: 
 Within the 7 days after the first dose of the infant series. Within the 7 days after the second dose of the infant series. Within the 7 days after the third dose of the infant series. Within the 7 days after the toddler dose. Incidence of AEs in the MDV group and in the PFS group from the first dose up to 1 month after the infant series.

	
 • Incidence of AEs in the MDV group and in the PFS group from the toddler dose up to 1 month after the toddler dose. • Incidence of serious adverse events (SAEs) in the MDV group and in the PFS group from the first dose up to 1 month after the toddler dose. • Incidence of newly diagnosed chronic medical conditions in the MDV group and in the PFS group from 1 month after the infant series up to the toddler dose.
Secondary Objective	Secondary Endpoints

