4.2. Exclusion Criteria

Subjects with any of the following characteristics/conditions will not be included in the study:

1. Infant who is a direct descendant (child, grandchild) of
 - Investigator site staff members directly involved in the conduct of the study, or
 - Site staff members otherwise supervised by the investigator, or
 - Pfizer employees directly involved in the conduct of the study.
2. Participation in other studies involving investigational drug(s) within 28 days prior to study entry and/or during study participation. Participation in purely observational studies is acceptable.
3. Previous vaccination with licensed or investigational pneumococcal conjugate vaccine.
4. A previous anaphylactic reaction to any vaccine or vaccine-related component.
5. Contraindication to vaccination with pneumococcal conjugate vaccine, or any other vaccine or vaccine component. Bleeding diathesis or condition associated with prolonged bleeding time that would contraindicate intramuscular injection.

6. Known or suspected immune deficiency or suppression, including known human immunodeficiency virus infection.
7. Major known congenital malformation or serious chronic disorder.
8. Significant neurological disorder or history of seizure including febrile seizure, or significant stable or evolving disorders such as cerebral palsy, encephalopathy, hydrocephalus, or other significant disorders. Does not include resolving syndromes due to birth trauma such as Erb's palsy.
9. Other acute or chronic medical condition including recent laboratory abnormality that may increase the risk associated with study participation or investigational product administration or may interfere with the interpretation of study results and, in the judgment of the investigator, would make the subject inappropriate for entry into this study.
10. Receipt of blood products or gamma globulin (including hepatitis B immunoglobulin and monoclonal antibodies, eg, Synagis).

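### Protocol 6.2 keeps a vaccinated child in safety follow-up when the parent stops the vaccine, but not when the investigator or sponsor withdraws the child for a new condition that meets an exclusion criterion

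*Protocol*

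**What the plan says.** The only primary objective is safety (Protocol 2). Two of its endpoints run well beyond the infant doses. The SAE endpoint begins "Incidence of serious adverse events (SAEs) in the MDV group and in the PFS group from the first dose up to 1 month after", and that window closes one month past the toddler vaccination. The chronic-condition endpoint begins "Incidence of newly diagnosed chronic medical conditions in the MDV group and in the PFS group from 1 month after the infant series", and that window closes at the toddler vaccination.

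Protocol 6.2 gives the investigator and sponsor discretion. If new information would exclude a child, "or the subject develops a condition or situation that would meet exclusion criteria, the subject may be considered for withdrawal". The visit checklists apply this at Visits 2, 3, 4 and 5. At Visit 4, for example, staff are told: "Ensure that the subject continues to be eligible for the study and meets none of the withdrawal criteria".

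The exclusion criteria in Protocol 4.2 include "Major known congenital malformation or serious chronic disorder", "Significant neurological disorder or history of seizure including febrile seizure" and "A previous anaphylactic reaction to any vaccine or vaccine-related component".

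Under its withdrawal-of-consent paragraph, Protocol 6.2 treats another group differently. Children whose parents ask to stop the product "will remain in the study and must continue to be followed for protocol-specified follow-up procedures", unless consent for further contact is specifically withdrawn. No equivalent sentence covers a child withdrawn by the investigator or sponsor.

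**The concern.** Several exclusion criteria describe conditions of the kind that the primary safety endpoints count. A child who develops one of them after vaccination can therefore leave the study because of a safety finding. Children with a new serious disorder may not have the same later risk as the rest, so the follow-up lost is not a random sample.

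The design is open-label, so each discretionary withdrawal is made with the vaccine group known, and the loss could differ between groups. The analysis would not correct for it. The SAP uses proportions of subjects, and it gives no rule for incomplete adverse event (AE) or SAE follow-up beyond the diary conventions and a reference to sponsor reporting standards (SAP 5.3.2).

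**Working it through.** **1. What is recorded before withdrawal.** At Visits 2 to 4 the checklist records AEs and SAEs before it checks eligibility. At Visit 5 it records SAEs and new chronic conditions first (Protocol 6.1.1.2 to 6.1.3.1). The safety population includes every child with at least one vaccination (Protocol 9.4; SAP 4.3). The triggering event is therefore counted.

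**2. What is required after withdrawal.** Protocol 6.2 asks for the reason, a final visit if applicable, follow-up of unresolved AEs, and efforts to document outcome. Protocol 8.1.4.1 follows known events until they resolve or stabilise. SAEs after active collection has ended are reported if the investigator learns of them. None of this requires anyone to ask about new SAEs or new diagnoses.

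**3. How the child is analysed.** The infant safety population needs one dose (SAP 4.3). SAEs up to 1 month after the infant series, and from then to the toddler dose, use that population (SAP 6.4.1). Chronic conditions use the infant or toddler population as relevant (SAP 6.1). A child withdrawn at Visits 2 to 4 stays in the infant denominator and, if no endpoint event has been recorded, appears event-free in intervals when no one was asking.

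**4. Time exposed.** Inputs are the visit windows in Protocol Table 1: Visit 1 at 42 to 72 days of age; Visits 2, 3 and 4 each 28 to 42 days after the previous visit; Visit 5 at 365 to 420 days of age; Visit 6 28 to 42 days after Visit 5.

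- Visit 4 age: 42 + 3×28 = 126 days to 72 + 3×42 = 198 days.
- Visit 4 to 5 gap: 365 − 198 = 167 days to 420 − 126 = 294 days.
- Smallest share: total time (365 + 42) − 72 = 335 days; 167/335 = 50%.
- Largest share: total time (420 + 28) − 42 = 406 days; 294/406 = 72%.

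These shares apply only to a child withdrawn by Visit 4.

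**5. The plan's own SAE figure.** Protocol Table 5 assumes 0.2% for any SAE with n = 150: 1 − (1 − 0.002)^150 = 25.9%, as printed. The expected number per arm is 150 × 0.002 = 0.3. The 0.2% comes from infant-series data and does not describe the later interval.

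**6. Illustrations, not estimates.** No withdrawal rate is given, so the rates below are assumptions.

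- Suppose 1% to 5% of an arm (1.5 to 7.5 children) are withdrawn before any SAE, and the full 0.2% risk falls after withdrawal. Lost cases: 1.5 × 0.002 = 0.003 to 7.5 × 0.002 = 0.015 per arm. At ten times that risk: 0.03 to 0.15.
- Loss unrelated to outcome, n = 147, 142 or 135 (about 2%, 5% or 10% lost): the detection probability is 25.5%, 24.7% or 23.7%.
- If 10%, 25% or 50% of first SAEs went unobserved, 1 − (1 − 0.002(1 − f))^150 gives 23.7%, 20.2% or 13.9%. Nothing in the documents suggests a loss near the top of this range.

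The documents give no planning incidence for new chronic conditions, so no figure can be put on that endpoint.

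**The case against.** The case on the other side is that the rule only permits withdrawal, that the outcome prompting it is already on the case report form, and that real safeguards exist. Withdrawal reasons are tabulated by group and withdrawals for AEs are listed (SAP 6.3.1), so unequal loss would be seen. The chronic-condition endpoint is also well protected for most children. No scheduled recheck falls between Visits 4 and 5, and a condition found in that interval is recorded at Visit 5 before eligibility is checked.

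All of that stands, and it limits the size of the problem. It does not close the gap. A table of withdrawal reasons shows who left, not what happened to them afterwards.

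A reader might go further and infer that withdrawing a child for an SAE could erase an arm's only case, a change of 1/150 = 0.67 percentage points. The documents do not support this. The endpoint is a proportion of subjects (SAP 5.2.1), so that child is already in the numerator and a second SAE would not alter it. A case is lost only if a child is withdrawn for something non-serious and the first SAE comes later.

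A reader might also infer that the Visit 4 eligibility check should go because no vaccine is given then. That does not follow. The check precedes a blood draw, the exclusion criteria include bleeding conditions, and eligibility bears on the evaluable population (SAP 4.1).

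**Conclusion.** The gap is real and narrow. For a vaccinated child withdrawn by the investigator or sponsor at Visits 2 to 4, the protocol does not require active collection of later first SAEs or of chronic conditions diagnosed between Visits 4 and 5. The child still counts as observed in the infant denominator. Any missed event lowers the reported incidence, and the loss could differ by group because allocation is known.

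The effect is probably small. Its size cannot be computed, because the documents give neither a withdrawal rate nor the risk in withdrawn children. The conclusion rests on reading 6.2 as withdrawal from the study, and on the absence of any other sentence requiring new-event collection after such a withdrawal. Endpoints that follow the toddler dose are not part of this point: a child who does not receive that dose is outside the toddler population whether or not follow-up continues. This is a cheap improvement to a safety study and not a threat to its main conclusions.

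**What to change.** In Protocol 6.2, extend the retention rule now written for parental requests to stopping initiated by the investigator or sponsor. Any child who has received at least one dose stays in follow-up, by contact, for SAEs and newly diagnosed chronic conditions to the end of the endpoint windows, unless the parent withdraws consent for further contact. For a child with no toddler dose, state that these windows end when Visit 5 (chronic conditions) and Visit 6 (SAEs) would have fallen due.

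Leave decisions on further doses, and the Visit 4 check, to the existing text.

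The cost is one paragraph in a protocol amendment and a few extra contacts for children no longer being vaccinated. No visits are added.
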